
**Cost Effectiveness:** To further inform utility of CHARM2, a cost-effectiveness analysis will be conducted under the direction of [name] using WHO-CHOICE methodology, an internationally accepted standard of economic analysis of health programs. Costs will be collected prospectively and include capital costs (e.g., equipment, space) and recurrent inputs (e.g., FP supplies, administrative costs). Given an expected outcome of improved contraception, costs of increases in non-CHARM2 FP services will be included as partner costs. Costs will be discounted at a rate of 3% per year, per WHO-CHOICE recommendations, varying from 0% to 6% in the sensitivity analysis. Drivers of variation in the total program cost will be assessed using multivariate linear regression. Cost-effectiveness will be calculated by dividing the total program costs by total health outcomes achieved over intervention duration. Outcome measures will include number reached by the CHARM2 and unintended births averted (based on outcome analyses). Based on prior research, we will use an estimate of 3.8 DALYs averted per unintended birth averted. We will also include quantitative measurements of other benefits from unintended pregnancy prevention (e.g., household savings and assets) to capture some of the spill over effects of when unintended pregnancies are prevented. Following WHO benchmarks, the intervention will be categorized as ‘very cost-effective’ if the cost per DALY averted is  $<1x$  the country’s per capita GDP. We will undertake a probabilistic sensitivity analysis, sampling each cost and outcome from an appropriate distribution to determine mean incremental cost-effectiveness, and assess drivers of uncertainty using ANCOVA. Findings will be used to support sustainability and scale up of CHARM2 for use in rural India and elsewhere.

**Sample size considerations:** Treatment effects detectable with 80% power given the 2-armed design with 20 clusters of 48 measurable couples (assuming 80% retention) per arm, or n=960 observed couples. Power calculations took into account multiple levels of clustering, both within-village and within-sub center variance.

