- a) Based on CHARM, we expect the proportion of women using modern contraception in the control group to be 40% at 18 month follow-up. This study will have 83.3% power to detect an absolute difference of 12% or more between treatment groups at follow-up, or 40% vs 52% in the two groups, with total kappa [variance]=0.10, assumed to be split equally between within-village variance and within-cluster variance . These values were found in the CHARM study.
- b) Based on CHARM, we expect that 89.2% of women in the control group will report no recent MSV at 18 month follow-up. We have 91.5% power to detect an absolute difference of 6% or more between treatment groups (89.2% vs. 95.2%) with kappa=0.036,

assumed to be split equally between within-village variance and within-cluster variance. The effect size of 6% difference and the kappa=0.036 were observed in the CHARM study.

c) Based on CHARM, we expect the proportion of women with no unintended pregnancy over 18 month follow-up to be 90% in the control group. This study will have 89.5% power to detect an absolute difference of 5.5% or more between groups (90% vs. 95.5%), with kappa=0. The effect size of 5.5% difference is based on a meta-analysis of cluster RCTs evaluating impact of FP interventions on unintended pregnancy (with comparable measures to this study). The study showed a 50% reduced risk for intervention participants with no unintended pregnancy in the CHARM group, or 5.5%. The kappa=0 is based on the CHARM study, where no significant intra-cluster correlation was found for this outcome.

While we will use longitudinal mixed effects logistic regression methods in our analyses, for power calculations we considered only the 18-month time point in a model similar to those to be used in the analyses. Power for the prescribed longitudinal analyses will be higher. Power calculations for each hypothesis used statistical simulations with 10,000 iterations. The conversion from kappa to the random cluster effect was done using the delta method, and was confirmed through the simulation.

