### **Importance of the Knowledge to be Gained**

Data collected from this project will be used to create program efforts that can be integrated into national rural health and family planning policies and initiatives, with the goal of improving family planning and reducing unintended pregnancy at a population level.

**Interim Safety and Efficacy Review.** Study risks are low. However, we will convene a Data and Safety Monitoring Board (DSMB) to review safety on a yearly basis. The study will be stopped early if there are serious safety concerns or early evidence of a large beneficial treatment effect. An interim efficacy analysis will be conducted after half of subjects (n=10 geographical clusters) have completed the 18 month visit. The O'Brien-Fleming stopping rule for efficacy will be used. Because validation of the proposed CHARM2 intervention is scientifically important independent of statistically significant results, there will be no futility analysis. The DSMB will consist of experts on FP, MSV and clinical trials in India.

**Confidentiality and Security.** Data security and confidentiality are critically important due to the sensitive subject matter of this study. All participant identifiers such as name, address or telephone number will be maintained on separate forms in locked storage at NIRRH and kept separately from the analytic database. Data shared among NIRRH, Population Council, and UCSD will be maintained on password-protected and secure servers at each site. The data will be backed up nightly on the UCSD server.

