This study has moderate risk. The risks are reasonable in relation to benefits/knowledge gained. Serious risk is unlikely. Major risk is attached to the study's focus on sensitive topics such as family planning and sexual violence. As noted, a number of efforts have been undertaken to reduce risks for study participants. In addition, we have developed both internal and external data safety and monitoring procedures, and a plan to determine if halting of study procedures are required. These are as follows:

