With recognition of the high rates of male-perpetrated partner violence among young couples in rural India, special efforts will be made to prevent study involvement from inciting violence against wives. We will only include couples in which wives are allowed to participate and to participate in accordance with study design (private survey administration with wives). Male abuse and control behaviors will only be asked of wives and men will not be informed that wives will be assessed on these items; wives will be asked not to disclose survey questions and their responses to their husbands unless they feel very safe. The informed consent of the men serves as an agreement that the information researchers obtain from both men and their wives will remain confidential and would not be shared between investigators as well as between participants. In addition, the survey tools will be piloted to understand their sensitivity administering to both men and their wives; if any issues are identified, items will be revised or dropped accordingly. Notably, survey items and procedures proposed are similar to those used in the NFHS-3 and previous couples research from Drs. [name] and [name]; these efforts assessed partner violence in couples and no adverse outcomes were observed. This approach also follows WHO guidelines for Domestic Violence research. To provide greater support for participants, both husbands and wives in each phase of study will receive referrals to health workers known for having good sensitivity on issues of partner violence and family planning options. If, despite all these precautions, we find that there is a violence happening as a result of study participation, we will make efforts to stop through the use of local village committees and health care workers. If we see an inability to stop the violence even after our efforts, a highly unlikely scenario, the study will be terminated. Identification of such issues will be noted as adverse events and reported accordingly to all investigators, NIRRH, UCSD, Population Council.

Based on the above rationale and the knowledge that is expected to result from this study to inform intervention practices and policy implications around family planning approaches in rural India, and our belief that the risks associated with this study are minimal in relation to the possible benefits to the broader community, we feel that there is an appropriate risk/benefit ratio for this study.

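### Violence is recorded as an adverse event only if attributed to participation, with no criteria given, and no stated route takes violence data to the DSMB

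*Combined protocol and SAP*

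**What the plan says.** **Section 18 (Risk/Benefit Ratio).** Action starts if "we find that there is a violence happening as a result of study participation". Efforts to stop the violence follow, and then: "If we see an inability to stop the violence even after our efforts, a highly unlikely scenario, the study will be terminated". On recording: "Identification of such issues will be noted as adverse events and reported accordingly to all investigators, NIRRH, UCSD, Population Council". The DSMB is not among the recipients. The text does not say who makes the finding or by what criteria.

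**Section 15 (Risk Management Procedures).** A wife who reports life-threatening violence is withdrawn and given supported referral, whatever the cause. The passage does not call this an adverse event.

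**Section 15 (Interim Safety and Efficacy Review).** A DSMB that includes MSV expertise reviews safety each year. "The study will be stopped early if there are serious safety concerns or early evidence of a large beneficial treatment effect". The safety limb is not defined. The only boundary specified is O'Brien-Fleming, for efficacy.

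**Section 14 (Potential Risks).** The assessments ask wives about physical as well as sexual violence from husbands. CHARM2 wives are also asked about MSV in their intervention sessions.

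**Section 9 (Sample size considerations, item b).** "we expect that 89.2% of women in the control group will report no recent MSV at 18 month follow-up".

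**The concern.** Section 18 expects that study involvement could provoke violence, but a case enters the safety record only after someone has decided that participation caused it. Where violence is common without any intervention, that decision is often a guess. If doubtful cases are called background, harm is under-recorded. If they are blamed on the sessions, background violence is counted as harm. The plan defines no procedure, so neither error rate can be known.

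The DSMB is the body meant to review safety, yet no passage sends it violence reports or by-arm violence data. Both arms are surveyed at baseline, 9 and 18 months, so a comparison is possible at little cost. The plan uses these data only to test whether MSV falls. Physical violence appears in none of the hypotheses or power calculations. Withdrawing women who report life-threatening violence may also remove the most severe cases from later surveys, so those events need a count of their own.

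**Working it through.** **Inputs**
- Control wives reporting no recent MSV at 18 months: 89.2% (section 9, item b).
- Planned effect, kappa and power: "We have 91.5% power to detect an absolute difference of 6% or more between treatment groups (89.2% vs. 95.2%) with kappa=0.036".
- Observed sample: "20 clusters of 48 measurable couples (assuming 80% retention) per arm, or n=960 observed couples". Since 20 × 48 = 960, I read this as 20 clusters in total, that is 10 clusters and 480 couples per arm. The interview sample agrees: 50 couples at 5 per intervention cluster gives 10 clusters.
- Two-sided 5% is assumed, because no alpha is stated.

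**The plan's own figure.** Read kappa as a between-cluster coefficient of variation of the MSV rate.
- Variance per cluster pair = 0.892 × 0.108/48 + 0.952 × 0.048/48 + 0.036² × (0.108² + 0.048²) = 0.002977.
- With one cluster per arm subtracted, z = √(9 × 0.06²/0.002977) = 3.30, and power = Φ(3.30 − 1.96) = 91.0%, against 91.5% stated. Without the subtraction it is 93.5%.
- Read instead as an intracluster correlation (ICC), kappa gives a design effect of 1 + 47 × 0.036 = 2.69 and power of 56.1%.

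The match therefore depends on what kappa means, so both readings are carried forward.

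**Background**
- 1 − 0.892 = 0.108.
- Observed, per arm: 480 × 0.108 = 51.8 women.
- Enrolled, per arm: 600 × 0.108 = 64.8 women.

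This rate covers recent MSV only. The documents give no background rate for all violence.

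**Can single cases be sorted?** Assume harm of 6 points, the planned benefit reversed: 10.8% + 6% = 16.8%.
- CHARM2 cases: 480 × 0.168 = 80.6. Excess: 80.6 − 51.8 = 28.8.
- Share due to the study: 28.8/80.6 = 36%, so about 64% would be background.
- For assumed rate ratios of 1.25, 1.5 and 2.0, the study-related share, (RR − 1)/RR, is 20%, 33% and 50%.

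Even if the rate doubled, half the CHARM2 cases would have occurred anyway.

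**What would a by-arm table detect?** For 10.8% against 16.8% with 480 per arm:
- SE = √(0.108 × 0.892/480 + 0.168 × 0.832/480) = 0.0222.
- Ignoring clustering: z = 0.06/0.0222 = 2.70, power = Φ(2.70 − 1.96) = 77%.
- Design effect 2.69: z = 2.70/√2.69 = 1.65, power = Φ(1.65 − 1.96) = 38%.

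Over the same range of design effects, power is 25% to 12% at RR 1.25, 69% to 32% at RR 1.5, and 99.5% to 79% at RR 2.0. Yearly reviews during 2.5 years of rolling enrolment would have fewer than 480 per arm, so early power is lower.

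**The case against.** Several stronger readings are tempting, and the documents do not support them.

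- **That violence can end the study only if it is attributed to participation.** The Interim Safety and Efficacy Review is a separate route with no attribution condition. The limit applies only to section 18's own clause, which also requires that the violence could not be stopped.
- **That unblinded staff make the judgement.** Section 11 says research staff are not blinded, but section 18 says only *we* and identifies no assessor.
- **That cause can never be known from a case.** Section 14 describes a specific mechanism, a husband learning of his wife's disclosure. A wife may be able to report that trigger herself. Attribution is often unreliable, not always impossible.
- **That by-arm data are the only data that can show harm.** Both arms have surveys and pregnancy tests. Violence provoked by either would occur in both arms, and a comparison between arms could miss it. Suspected cause is therefore worth keeping as information.
- **That an increase in MSV would go unseen.** The primary analysis compares MSV by arm at 9 and 18 months, and nothing makes the test one-sided. The gaps are timing (outcome analysis is set for month 40) and physical violence.
- **That the halting plan was never written.** Section 15 promises "a plan to determine if halting of study procedures are required. These are as follows", and no list follows in the text available. It may have been lost when the PDF was read, so it is not counted as an error.

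It is also fair to say that by-arm tables from 20 clusters are weak evidence. That stands. It argues for presenting them as material for DSMB judgement, not for withholding them.

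**Conclusion.** The concern holds within these limits. Section 18 makes adverse-event recording of violence, and its own termination clause, depend on an attribution with no assessor and no criteria. Against an expected 10.8% of control wives reporting recent MSV (about 52 of 480 observed), single cases often cannot be sorted reliably. Under an assumed 6-point increase, about 29 of 81 CHARM2 cases would be excess.

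The separate safety stop does not close the gap, because it is undefined and no passage says what violence data the DSMB receives. Life-threatening reports have no stated link to adverse-event recording, and no planned comparison covers physical violence.

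The conclusion about recording and reporting rests on the text alone. The counts rest on the plan's MSV rate and on 480 observed wives per arm. The power figures also rest on the assumed size of harm, two-sided 5%, and the reading of kappa. This should be corrected. It does not invalidate the design.

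**What to change.** 1. In section 18, record life-threatening reports under section 15, and violence reported outside the surveys, as safety events regardless of judged cause. Keep any suspected link to participation as a separate field, since harm from surveys or pregnancy tests would arise in both arms.
2. Add the DSMB to the section 18 reporting list.
3. Give each yearly DSMB review confidential by-arm tables of MSV and physical violence from the existing 9- and 18-month surveys, plus life-threatening reports by arm.
4. Reconcile section 18 with the two section 15 passages (Risk Management Procedures, and Interim Safety and Efficacy Review) on how the study would be stopped for safety. Any rule is for the sponsor and the DSMB to set.

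**Cost.** Amendment wording, a form field, and a by-arm table from data already collected. Survey-reported violence goes into the tables and does not become individual event reports, which at 10.8% would be about 65 per arm of 600 for MSV alone.

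**Downsides.** The tables will be noisy, most of all early on. CHARM2 wives have extra chances to disclose in sessions, so counts from outside the surveys are not directly comparable between arms. The DSMB also gains extra unblinded looks at a hypothesised outcome, so the tables should be labelled as safety review only.

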## **19. EXPENSE TO PARTICIPANT**

Subjects will not incur any expenses during the course of, and as a result of their participation in the study.

## 20. COMPENSATION FOR PARTICIPATION

Subjects will not be compensated financially for their participation.

### **24. BIOLOGICAL MATERIALS TRANSFER AGREEMENT**

There will be biological materials collected for this study, as urine samples will be collected from women in the study. However, the material will be moved from our local field site to a laboratory that is part of our partnering institution (NIRRH) as part of the study. Therefore, we don't believe that a Biological Materials Transfer Agreement (BMTA) is necessary.

### **25. INVESTIGATIONAL DRUG FACT SHEET AND IND/IDE HOLDER**

This study does not involve any investigational drugs.

### **26. IMPACT ON STAFF**

There is no need for additional training of UCSD staff for the purposes of this study.

### **27. CONFLICT OF INTEREST**

Neither the PI nor any key personnel associated with this study have any financial interests or other "conflicts" related to this study.

### **28. SUPPLEMENTAL INSTRUCTIONS FOR CANCER-RELATED STUDIES**

This project does not qualify under the California Clinical Trial Law.

### **29. OTHER APPROVALS/REGULATED MATERIALS**

Approval from other UCSD review committees is not necessary for this project.

### **30. PROCEDURES FOR SURROGATE CONSENT AND/OR DECISIONAL CAPACITY ASSESSMENT**

Not Applicable.

Version date: Nov 15, 2016
